6.7.4 Adverse Device Effect (ADE)

An adverse event related to the use of an investigational device.

Note: This definition includes adverse events resulting from insufficient or inadequate instructions for use, deployment, implantation, installation, or operation, or any malfunction of the medical device.

Note: This definition includes any event resulting from the use error or from intentional misuse of the medical device.

6.7.5 Serious Adverse Device Effect (SADE)

Adverse device effect that has resulted in any of the consequences characteristic of a serious adverse event.

6.7.6 Unanticipated Serious Adverse Device Effect (USADE)

A serious adverse device effect which by its nature, incidence, severity or outcome has not been identified in the current version of the risk analysis report.

6.7.7 Anticipated Serious Adverse Device Effect (ASADE)

A serious adverse device effect which by its nature, incidence, severity or outcome has been previously identified in the risk analysis report.

6.7.8 Procedure for assessing, recording and reporting adverse events, adverse device effects, serious adverse events and serious adverse device effects

Safety surveillance and reporting will be done for all subjects enrolled in this investigation as described below.

Safety surveillance within this investigation (and the safety reporting performed by the investigator), starts as soon as the subject is enrolled in this investigation (date of signature of the informed consent form). The safety surveillance and the safety reporting will continue until the last investigational visit has been performed or the subject is deceased or the subject/investigator concludes his participation into the investigation.

For the purpose of this trial, all Serious Adverse Events and all Adverse Device Effects (regardless of severity) are to be documented and reported to the sponsor immediately and no later than 72 hours after becoming aware of the event.

Adverse events will be assessed by the investigator for relationship to the device and to the procedures involved.

- Procedure related: The AE is deemed related to the procedure if it occurred during the procedure or is directly linked to the procedure but was not directly caused by the medical device.
- Device related: The AE is deemed device related if it was directly caused by the medical device.

Investigators are responsible for promptly reporting all SAEs and ADEs to the sponsor by completing the Adverse Event form in the eCRF. All unresolved AEs should be followed by the investigator until resolution is reached.

Note: Refer to Table 1 'Data Collection' and Appendix D 'Data Collection Method'. In case of EDC failure, notify Sponsor via fax ([contact]) or e-mail ([contact]).

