- Subject has active systemic infection
- Subject has known renal arteries with diameter(s) < 4 mm
- Subject has an estimated GFR < 45 mL/min per 1.73 m² using the MDRD formula
- Subject had a renal transplant or is awaiting a renal transplant

Procedural Exclusions:

Subjects who have been enrolled in the study, and in whom the procedure was started, but do not have the EnligHTN™ Renal Denervation System enter their body, due to their anatomy, circumstances related to the procedure, or physician judgment will be classified as procedurally excluded. These subjects will be followed for 30 days post procedure. The reason for the procedural exclusion will be documented on the Procedural CRF.

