5.4 Follow-up visits

Subjects will return for follow-up at 1 month (± 14 days), 6 months (± 30 days) and at 12 months (± 60 days) post-procedure.

The following will be evaluated / reviewed according to Table 1:

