5.5 Clinical Investigation Termination

Each subject will be followed for 1 year post renal denervation procedure or until time of death, loss of follow up, withdrawal or clinical investigation termination. The clinical investigation will be complete after all follow-up visits are performed, all data is received by the Sponsor and the database is locked. The study will be closed when a final report is written on the conclusions and analysis of the data.

Participation in this clinical investigation is voluntary. Subjects are free to withdraw from the clinical investigation at any time without reason. A Clinical investigation Termination CRF should be completed by the site and provided to the Sponsor.

In a situation where a clinical investigation withdrawal is due to an adverse event the subject should be followed until resolution of that adverse event or determination that the subject's condition is stable.

Subjects must be informed about their right to withdraw from the investigation at any time and for any reason without sanction, penalty or loss of benefits to which the subject is otherwise entitled and withdrawal from the investigation will not jeopardize their future medical care or relationship with the investigator. Subjects will be asked to specify the reason for the termination, but have the right not to answer.

The investigator may decide to withdraw a subject from the investigation at any time. The subject's future care will not be influenced by a decision, voluntary or otherwise, to withdraw from the investigation. All reasonable efforts should be made to retain the subject in the clinical investigation until completion of the investigation.

Other reasons for termination or withdrawal include, but are not limited to, the following:

- Subject did not meet the inclusion/exclusion criteria
- Subject death (in case of subject death, the cause must be documented)
- Subject and/or family request
- Subject non-compliance
- Subject lost to follow-up, defined as the following: a subject will be considered "lost to follow-up" after a minimum of 2 documented phone calls of a physician or delegate at the study site to the subject or emergency contact and a certified letter sent to the last known address
- Subject's participation terminated by Investigator
- Study terminated by SJM
- The study terminated according to locally applicable regulations

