8.4.2 Secondary objectives analysis

Acute (30 days post procedure)

- Safety
The percentage of subjects with peri-procedural events within 30 days post procedure will be computed as follows:

$$\frac{\text{Number of subjects with peri procedural events within 30 days post procedure}}{\text{Number of subjects that underwent the procedure}} * 100$$

- Performance
The mean reduction in office Systolic and Diastolic Blood Pressure at 1 month and the mean reduction in ambulatory Systolic and Diastolic Blood Pressure at 1 month will be calculated in a similar way as described for the primary objective (Section 8.4.1). The percentage of subjects achieving office Systolic Blood Pressure < 140 mmHg at 1 month will be computed as follows:

$$\frac{\text{Number of subjects achieving office SBP < 140 at 1 month}}{\text{Number of subjects with data available at 1 month}} * 100$$

Mid to long term (6 and 12 months)

- Safety
Renal function change based on eGFR will be summarized by:
 1. Computing the change of the eGFR at 6 and 12 months, compared to baseline for each patient with data available at both time points.
 2. Calculating the mean and standard deviation of the eGFR change at those intervals

Assessment of renovascular safety as measured by occurrence of new renal artery stenosis (> 50%) and aneurysm at the site of ablation per Renal Artery Imaging will be summarized at 6 months as a percentage of subjects who have stenosis (> 50%) or aneurysm.
- Performance

The mean reduction in office Systolic Blood Pressure at 12 months, the mean reduction in office Diastolic Blood Pressure at 6 and 12 months and the mean reduction in ambulatory Systolic and Diastolic Blood Pressure at 6 and 12 months post denervation will be calculated in a similar way as described for the primary objective (Section 8.4.1).

Percentage of subjects achieving office Systolic Blood Pressure < 140 mmHg at 6 and at 12 month will be computed as follows:

$$\frac{\text{Number of subjects achieving office SBP} < 140 \text{ at 6 months}}{\text{Number of subjects with data available at 6 months}} * 100$$

$$\frac{\text{Number of subjects achieving office SBP} < 140 \text{ at 12 months}}{\text{Number of subjects with data available at 12 months}} * 100$$

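### Adverse-event reporting stops when a treated subject leaves, but the 30-day safety percentage still divides by all treated, so early leavers with no recorded event count as event-free

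*Combined protocol and SAP*

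**What the plan says.** Section 6.7.8 starts surveillance at consent and ends it at the last visit "or the subject is deceased or the subject/investigator concludes his participation into the investigation". Nothing there ties the end to a minimum time after the ablation.

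Section 5.5 makes early exit possible on either side. "Subjects are free to withdraw from the clinical investigation at any time without reason", and the investigator may also withdraw a subject at any time. Where a "withdrawal is due to an adverse event the subject should be followed until resolution of that adverse event" (or until the condition is stable). Section 6.7.8 adds that unresolved adverse events are followed to resolution, and section 6.8.1 requires subject deaths to be reported.

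Section 8.4.2 defines the acute safety result as a percentage. The numerator is the "Number of subjects with peri procedural events within 30 days post procedure" and the denominator is the "Number of subjects that underwent the procedure". Section 8.4 gives no rule for incomplete observation: no censoring, no time-to-event estimate and no sensitivity analysis. The 1-month blood pressure responder percentage in the same section uses a different base, the "Number of subjects with data available at 1 month".

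For procedurally excluded subjects, in whom the system never entered the body, section 4.5 says: "These subjects will be followed for 30 days post procedure".

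**The concern.** An all-treated denominator gives an unbiased 30-day percentage when every treated subject's event status is known through day 30. Here the plan itself ends the collection of events for anyone whose participation is concluded sooner. The provisions for unresolved events and for withdrawals caused by an adverse event cover events already known at exit. A new non-fatal SAE or ADE on day 20, in a subject withdrawn on day 10, falls outside the reporting duty.

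The error can go only one way, because a missed event lowers the percentage and nothing in the formula offsets it. It also leaves no trace: the reported figure is the same whether no subject or 25 subjects left early without an event. Safety is part of the study's stated purpose (section 4.1), and this is the only adverse-event percentage planned.

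**Working it through.** **The plan's own figures.** The documents state no expected value for the 30-day safety percentage, so there is nothing to reproduce for it. The sample size in section 8.2 does reproduce: (1.96 × 24.7 / 2.35)² = 424.4, rounded up to 425, and 425 / 0.85 = 500. It is not affected by this point. It supplies N = 500 treated and an attrition allowance of 15%, which is tied to the 6-month primary objective and not to day 30.

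**Formula.** Let

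- p = true 30-day event rate,
- q = share of treated subjects who leave before day 30,
- f = share of the leavers' 30-day events that fall after exit.

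If leavers have the same underlying risk as the others, the expected reported percentage is p × (1 − q × f). The shortfall is p × q × f, and the relative shortfall is q × f. The documents give none of p, q or f, so all three are assumed over a range.

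| q (leavers of 500) | f | true 5% reported as | true 10% reported as |
|---|---|---|---|
| 1% (5) | 0.2 | 4.99% | 9.98% |
| 1% (5) | 1.0 | 4.95% | 9.90% |
| 5% (25) | 0.2 | 4.95% | 9.90% |
| 5% (25) | 1.0 | 4.75% | 9.50% |
| 15% (75), extreme | 1.0 | 4.25% | 8.50% |

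For q of 1-5% the shortfall runs from 0.05 × 0.01 × 0.2 = 0.01 points to 0.10 × 0.05 × 1 = 0.50 points. In relative terms that is 0.01 × 0.2 = 0.2% to 0.05 × 1 = 5%. Even if the whole 15% attrition fell before day 30, the shortfall at p = 10% would be 0.10 × 0.15 × 1 = 1.5 points.

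**What the reader cannot see.** Suppose 25 subjects have recorded events and L others leave before day 30 without one. The plan's formula gives 25/500 = 5.0% for any L. Counting every such leaver as an event gives (25 + L)/500: 6.0% for L = 5, 7.0% for L = 10 and 10.0% for L = 25. Without L, the width of this interval is unknown.

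**Checking the obvious replacement.** One could divide only by subjects who had an event or were observed to day 30. Take 500 treated, p = 5% and 25 leavers at the same risk, so 25 × 0.05 = 1.25 expected events among them.

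- f = 0.2: 0.25 events are missed and 24.75 recorded. The plan gives 24.75/500 = 4.95%. The replacement gives 24.75/(475 + 1.00) = 5.20%, an error four times as large in the other direction.
- f = 0.5: 24.375 recorded. The plan gives 4.875%; the replacement gives 24.375/(475 + 0.625) = 5.125%. The errors are equal.
- f = 1: the plan gives 23.75/500 = 4.75%; the replacement gives 23.75/475 = 5.00%.

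The replacement keeps leavers with events and drops those without, so it is biased upward unless all the leavers' events come after exit. It is closer to the truth than the plan only when f exceeds one half.

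**The case against.** The strongest reply is that dividing by all treated is a common choice for events reported as they occur, and that the gap touches few subjects. Section 6.7.8 requires SAEs and ADEs within 72 hours of awareness, not only at visits. Section 5.4.7 asks at each visit about events since the last one. Section 5.5 asks for all reasonable efforts at retention, and requires at least two documented calls and a certified letter before a subject counts as lost. Section 6.4 declares limited adverse-event reporting as an exception for this study. All of this stands, and it is why the expected bias is small. None of it reaches a new non-fatal event after participation has been concluded.

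A reader might also infer more than the documents support:

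- *A large understatement.* Assuming that 5% leave and 30% of them have a later event gives 1.5 points, or 30% of a true 5% rate. That puts the leavers' risk at six times the cohort's, and nothing in the documents suggests it. With equal risk, the most that 5% leavers can remove from a 5% rate is 0.25 points.
- *Better protection for unexposed subjects.* The 30 days in section 4.5 is the planned follow-up length for procedurally excluded subjects, against 1 year for treated subjects. It is not a guaranteed minimum, and those subjects may also withdraw earlier.
- *A double standard between efficacy and safety.* The responder percentages need a measured pressure, so a data-available base is natural there. The contrast does not by itself show a fault.
- *A systematic gap after an early 1-month visit.* The window allows that visit at about day 30 − 14 = 16. Subjects who return later are asked about the interval; only those never reached again lack active enquiry.
- *No other safety percentage.* Section 8.4.2 also plans a 6-month percentage with stenosis or aneurysm. The point concerns adverse events only.

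**Conclusion.** The concern holds as a gap in how the 30-day percentage is ascertained and defined. Sections 6.7.8, 5.5 and 8.4.2 together count a treated subject who leaves before day 30 with no recorded event as event-free. Subjects with an event recorded before exit, including death, are already in the numerator and are not affected.

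The direction is certain; the size is not. It is about 0.01 to 0.50 percentage points if 1-5% leave early, the true rate is 5-10%, 20-100% of leavers' events fall after exit, and leavers have the same risk as others. If leavers have higher risk, the shortfall rises in proportion. If peri-procedural events cluster close to the ablation, it lies towards the lower end. The change is worth making because it is cheap, removes most of a one-directional error and makes the remainder visible. The expected distortion is not large.

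**What to change.** **Section 6.7.8.** State that for every subject with device entry, SAE and ADE reporting continues to at least day 30 after the procedure despite withdrawal by the investigator or sponsor, unless the subject withdraws consent to data collection. Reconcile section 5.5 with this, since it now carries follow-up past withdrawal only for the event that caused it.

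**Section 8.4.2.** Keep the all-treated denominator. Report beside it the number of subjects treated but not observed to day 30. Add one sensitivity analysis: either a Kaplan-Meier 30-day estimate with early leavers censored at exit (which assumes that leaving is unrelated to risk), or a worst-case bound that counts each unobserved leaver as an event. Do not replace the denominator with subjects who had an event or were observed to day 30.

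**Cost.** One sentence in 6.7.8, a matching edit in 5.5, one reported count and one extra estimate. In practice this means a record check or phone contact for the few early leavers, and possibly a slightly higher reported rate. No treatment or study procedure changes.

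### The device-relatedness rule in section 6.7.8 is narrower than the ADE definition in 6.7.4, so some non-serious use-related events may go unreported

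*Combined protocol and SAP*

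**What the plan says.** Section 6.7.4 defines an ADE as "An adverse event related to the use of an investigational device". Two notes widen it. The first brings in "adverse events resulting from insufficient or inadequate instructions for use, deployment, implantation, installation, or operation, or any malfunction of the medical device". The second adds: "This definition includes any event resulting from the use error or from intentional misuse of the medical device".

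Section 6.7.8 tells the investigator how to judge relationship. It begins with "Adverse events will be assessed by the investigator for relationship to the device and to the procedures involved" and then gives two rules:

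- The rule for the device reads: "Device related: The AE is deemed device related if it was directly caused by the medical device".
- The rule for the procedure covers any event that "occurred during the procedure or is directly linked to the procedure but was not directly caused by the medical device".

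The same section obliges the investigator to report all SAEs and all ADEs, whatever their severity, within 72 hours. It sets no reporting duty for a non-serious event that is not an ADE. Sections 6.7.5 and 6.7.6 build the serious ADE (SADE) and the unanticipated SADE (USADE) on the ADE.

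Two other sections matter. Under 13.1 the sponsor reviews the investigator's assessment and makes its own written determination of seriousness and relationship to the device. Under 8.4.2 the acute safety result is the percentage of subjects with a peri-procedural event within 30 days, out of those who underwent the procedure.

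**The concern.** *Related to the use of the device* and *directly caused by the device* are different tests, and the second is narrower. The protocol gives investigators only the second as a working rule. It does not say that a use-related event within 6.7.4 still counts as device related under 6.7.8.

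The gap is relevant to this procedure. Section 5.2 describes operator decisions throughout: choosing the basket size, positioning the tip, opening the basket, and choosing where and how often to ablate. An event traced to one of these steps falls within 6.7.4, yet an investigator could reasonably see it as procedural under 6.7.8.

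What is at stake is first the capture of non-serious events and then the labelling of serious ones. Non-serious events are to be expected: the Background section reports minor peri-procedural events in the feasibility study (vasospasm, haematoma, vasovagal episodes) that were attributed to the device or the procedure.

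**Working it through.** The protocol states no figure on this point and no arithmetic decides it. The check sets the passages side by side and follows an event through to the analysis.

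**Step 1. Compare the two tests by type of event.**

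| Type of event | ADE under 6.7.4? | Device related under 6.7.8? |
|---|---|---|
| The device itself directly injures the subject, with or without operator error | Yes | Yes |
| The event results from how the device was used or operated, or from its instructions, and the investigator does not judge the device to be the direct cause | Yes | No; procedure related if it happened during the procedure or is directly linked to it |
| The event is linked to the procedure but not to use of the device (for example, due only to the contrast medium) | No | No |

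The tests disagree only in the second row.

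**Step 2. Follow a second-row event through the reporting duty in 6.7.8.**

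| | Recognised as an ADE | Not recognised as an ADE |
|---|---|---|
| Serious | Reported; SADE, and USADE if unanticipated | Reported as an SAE; SADE or USADE status depends on the sponsor's review |
| Non-serious | Reported | No duty to report |

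The lower right cell is the exposure in capture. Sections 5.2, 5.3 and 5.4.7 have adverse events noted in the hospital records, but send reporting back to 6.7.8. Such an event can therefore sit in the hospital file without reaching the sponsor.

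**Step 3. Follow it to the planned analysis.** The measure in 8.4.2 is

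percentage = 100 × (subjects with a peri-procedural event within 30 days) / (subjects who underwent the procedure).

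It is not split by relationship to the device, but its numerator can hold only events that were reported. A subject whose only such event falls in the lower right cell drops out of the numerator and stays in the denominator. The effect can only lower the percentage. With the planned 500 treated subjects, each one lost lowers it by 100 × 1/500 = 0.2 percentage points.

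**Step 4. Can the number of such subjects be found?** No. The documents give neither an ADE rate nor the share of events that are use-related without direct causation by the device.

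**The case against.** The strongest reply is that the reporting duty attaches to ADEs, a term defined in 6.7.4, and that SADE and USADE are built on the same term. Nothing says that the *device related* label in 6.7.8 decides ADE status. Read strictly, a use-error event remains a reportable ADE whatever label it carries. This stands. Misclassification is a risk created by two inconsistent texts, and is not an outcome that the protocol prescribes.

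Four further replies also have weight:

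- **The labels need not exclude each other.** Section 6.7.8 asks about both relationships, and the closing clause of the procedure rule may limit only its second limb. The sentence is ambiguous. The device rule is too narrow on either reading.
- **Many injuries by the catheter or basket are directly caused by the device**, even when the operator erred. They stay device related, so the affected class is smaller than all use-related harm.
- **The sponsor re-determines relationship** (13.1), and 13.2 requires source documentation to support this. For serious events that is a real safeguard, though no separate criterion is given. It cannot act on an event that was never reported.
- **Section 6.4 openly declares limited adverse event reporting.** That explains why non-serious events unrelated to the device are left out. It does not cover ADEs, which 6.7.8 keeps reportable at every severity.

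A reader might infer that use-error, deployment and operation events are all labelled procedure related and so drop out of the ADE, SADE and USADE counts, leaving the device safety result biased low. The documents do not support this. ADE status is still set by 6.7.4, some of these events meet the direct-cause rule, and section 8 plans no ADE, SADE or USADE rate that could be shown to change.

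**Conclusion.** The inconsistency is real and should be resolved. The rule in 6.7.8 is narrower than the definition in 6.7.4, and investigators who apply it could treat some use-related events as procedure related and not as ADEs. For non-serious events the possible result is that they do not reach the sponsor and are missing from the 30-day percentage in 8.4.2. For serious events reporting is secure, and only the SADE or USADE flag is exposed, unless the sponsor's review corrects it.

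The direction for the 30-day percentage is downward. The size cannot be stated, and any assumed ADE rate would describe a result that the plan does not compute. The conclusion assumes that at least some investigators let the 6.7.8 label guide whether an event is an ADE, which the text permits but does not require. The renal function and renal artery outcomes in 8.4.2 are not defined by this attribution.

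**What to change.** Amend 6.7.8 in three respects:

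1. Define *device related* as meeting the ADE definition in 6.7.4, including its two notes.
2. State that relationship to the device and relationship to the procedure are assessed independently and may both be answered yes.
3. In the procedure rule, which ends "directly linked to the procedure but was not directly caused by the medical device", delete everything from *but* onward.

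Since 13.1 gives the sponsor no criterion of its own, the revised definition can serve both the investigator's and the sponsor's assessment.

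The cost is a change to a few sentences. The adverse event form is not in the documents; if it forces a choice between the two relationships, it needs two separate items. The downside is that slightly more events will be reported as ADEs. The change is best made before further data collection, because a non-serious event left unreported at the time may be hard to recover later.
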